Analysis Plan: Pharmacokinetics of Advantage Arrest

NCT04184271

Document Date: 07/30/2020

For the pharmacokinetic analysis, baseline serum fluoride and silver concentrations will be assessed and when appropriate, subtracted from other timed serum concentrations to adjust for baseline levels.

Pharmacokinetic analysis will be performed using Phoenix WinNonlin (Certara).

- The time to peak concentration (T_{max}), observed and baseline-corrected peak concentrations (C_{max}), and observed 24-h concentration (C_{24 h}) will be reported.
- The elimination rate constant (k_{elim}) will be determined by nonlinear regression with a minimum of 3 time points with decreasing concentrations over time observed after the peak concentration.
- Half-life (t_{1/2}) will be calculated as ln(2)/k_{elim}.
- Area under the curve (AUC): The 24-hour AUC (AUC_{0-24 hr}) will be calculated using a log-linear trapezoidal rule of baseline-corrected serum concentrations from time = 0 to 24 h. The AUC_{0-∞} will be calculated using a log-linear trapezoidal rule of baseline-corrected serum concentrations and extrapolated to infinite time by C_{24hour}/k_{elim}, where C_{24hour} is the 24 hour concentration.
- The percent extrapolated AUC will be calculated as $(AUC_{0-\infty} AUC_{0-24 \text{ hr}})/AUC_{0-\infty} \times 100$.
- The total urinary recovery of fluoride and silver will be determined by multiplying the concentration measured in the urine collected over 24 hours by the total volume of urine collected over 24 hours.

Statistical analysis will be performed using Excel to calculate the mean \pm standard deviation for the pharmacokinetic parameters. No statistical comparisons will be made as it is a single arm study.

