Protocol: Pharmacokinetics of Advantage Arrest

Protocol version: 2016-11-08 NCT04184271 Document Date: 11/08/2016

Sponsor:	Advantage Silver Dental Arrest, LLC [name] United States
Investigator:	[name] University of Washington [name] United States Email: [contact] [contact]
Sub-investigators:	[name] University of Washington [contact]
	[name], PhD University of California, San Francisco [contact]
Research Site:	University of Washington Regional Clinical Dental Research Center [name] United States [contact]
Regulatory Monitor:	[name] Cooley Consulting, Inc. [name] United States [contact]

Purpose of the Study and Background

Objective: The purpose of this study is to characterize basic PK parameters (Cmax, $t_{1/2}$, AUC, and total urinary recovery) to contribute to evidence for the safety of Advantage Arrest, consistent with Guidance for Industry--Exposure--Response Relationships (April 2003). On a preliminary basis, we will also characterize the microbiome before and 24-hours after the topical treatment.

Background: The Sponsor/Investigator conducted a preliminary PK study in six adults (Vasquez et al., 2012) in which 38% diammine silver fluoride (silver diamine fluoride) was applied topically to three teeth in each subject and maximum serum concentration and time to maximum serum concentration were studied over four hours. Mean amount of the agent applied was 7.57 mg. Over the four-hour observation period the mean maximum serum concentrations were 1.86 umol/L for fluoride and 206 nmol/L for silver. These maximums were reached at 3 h and 2.5 h for fluoride and silver, respectively. Fluoride exposure was below the EPA oral reference dose. Silver exposure exceeded the EPA oral reference dose for cumulative daily exposure over a lifetime, but for occasional use was well below concentrations associated with toxicity. Nevertheless, the number of subjects was limited and the follow-up period too short to calculate the AUC. Although diammine silver fluoride is available in many countries, there are no other published PK studies to our knowledge.

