Assumptions: This is a topical agent where the active ingredients are applied to the teeth and eventually swallowed and may be absorbed through the GI tract or excreted. Minimal amounts are absorbed through the oral mucosa. Serum concentrations of silver and fluoride will be be proportional to the dose of silver and fluoride administered topically to the teeth as part of Advantage Arrest. The total urinary recovery of fluoride, adjusted for baseline levels, will be calculated to estimate the minimum amount absorbed in each patient following application of the varnish. As biliary excretion is the principle route of elimination of silver (Lansdown et al., 2010), it is unlikely that significant amounts of silver will be recovered in the urine.

Criteria for Subject Selection

Number of subjects: There will be up to 20 healthy adult subjects enrolled in the study with the goal of at least 16 subjects to complete the study.

Gender of subjects: The subjects will be approximately half male and half female. **Age of subjects:** Subjects must be 18 years of age or older.

Racial and Ethnic Origin: In a small study it is not possible to fully represent the racial/ethnic distribution of the region or US. The investigator will attempt to recruit a racial/ethnic diverse population.

Inclusion criteria: Subjects will have at least 20 teeth. Subjects will be healthy and taking no prescription or OTC medications, including topical fluoride gels or rinses. Healthy status will be determined by self-reported medical history by the attending clinician.

Exclusion criteria: Subjects will be excluded if they have oral mucositis or any ulcerative lesions or hypersensitivity to silver or fluoride. Subjects who are pregnant, breastfeeding, or weigh less than 110 pounds will not be eligible to participate.

Methods and Procedures

Design of the Study and Minimization of Bias: Open label exposure--response study.

Randomization: Not applicable

Blinding: Not applicable

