Baseline procedures: When informed consent has been obtained, age, race, gender, and ethnicity information will be collected at baseline along with a brief health history. A brief visual examination will be conducted to note any evidence of inflammatory or ulcerative changes to the gums or other oral tissues. Non-fluoride toothpaste will be used on the day of the baseline appointment through the 24-hour blood draw period. An 18 gauge sterile venous cannula will be placed in an upper extremity. An initial blood sample of 6 mL (one tube for serum collection) will be withdrawn using a fluoride free tube (BD Vacutainer with Clot Activator Plus Royal Blue Stopper). Subject will void for a baseline urine sample collection. Using a dental microbrush, dental plaque will be collected from the buccal surfaces of the upper posterior teeth and the microbrush inserted in a sampling tube and agitated.

Study intervention: Advantage Arrest, Aqueous Diamine Silver Fluoride [Ag(NH₃)]₂F, CAS RN 33040-28-7, 38.3% to 43.2% in purified water 5.0 - 5.9% (w/v) fluoride; 24.4 - 28.8% (w/v) silver, Silver Diamine Fluoride

Teeth will be brushed with a soft toothbrush to remove debris and dried with cotton prior to application. The specific procedure is that 5 mg (1 drop) of Advantage Arrest will be dispensed into a plastic dappen dish and all of the material will be applied to the facial cervical surfaces of 5 posterior teeth with an applicator. To calculate the amount of Advantage Arrest applied: the dappen dish with the initial amount of Advantage Arrest dispensed and applicator will be weighed before application and after application. The amount applied will be calculated as the difference in weights before and after application. The amount applied will be recorded. The teeth will remain isolated with cotton rolls for 3 minutes and then rinsed with water and high volume evacuation. Subjects will not eat for at least 2 h following application of the test agent.

Blood, urine and plaque sampling following intervention:

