Subjects will have blood samples of 6 mL withdrawn at 30 min, 1h, 2h, 3h, 4h, 6h, 8h, 12h and 24 hours. Urine will be collected for a 24-hour cumulative sample following application of the study intervention. Subjects will continue to collect urine in the original container until 12h and be provided instructions and a container to continue the urine collection to 24 hours. Subjects will remain at the research site through the 12 hour blood and urine collection and return for the 24-hour timepoint. A 24-hour plaque sample will be obtained in the same manner as the baseline sample.

Blood, urine and plaque sample processing:

Blood samples will be spun in a clinical centrifuge, the serum withdrawn, and then the serum will be frozen for later analysis. The total volume of urine at baseline, 12 and 24 hours will be recorded and a 10 mL aliquot will be taken of each sample and frozen for later analysis. Plaque samples will be placed in a receiving tube, the tube agitated, and the contents frozen for later analysis.

Sample Analysis: Serum and urine samples will be analyzed for F- by ion chromatography and Ag+ by ICPMS (Inductively coupled plasma mass spectrometry). Cmax, Tmax, Cmin (last measurable time point), $t_{1/2}$, and the AUC will be calculated from serum samples. Total amount recovered will be calculated from urine samples. Plaque will be analyzed by 16S ribosomal RNA profiling.

Data Analysis and Monitoring:

Subject disposition: The frequency and reason for subject withdrawal will be summarized.

Data Analysis and reporting: The PI and sub-investigators will be responsible for performing all analyses, creating the output for the analyses and disseminating results to the study team. The Principal Investigator and the rest of the study team will then review the results. The Principal Investigator will be responsible for drafting and preparing a final report of the study.

Data Storage and Confidentiality

The data will be stored on password protected computers in the Clinical Research Center at the UWMC and in a locked cabinet and on password protected computers at the Regional Clinical Dental Research Center at the University of Washington School of Dentistry. Only investigative personnel will have access. The data will be available for inspection by regulatory monitors and FDA.

Risk-Benefit Assessment

Risk Category: Greater than Minimal Risk

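### The SAP's urinary recovery formula subtracts no baseline, although the protocol promises a baseline-adjusted fluoride recovery as the estimate of minimum absorption

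*SAP*

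**What the plan says.** The protocol's Objective lists total urinary recovery among four PK parameters, with Cmax, half-life and AUC. Its Assumptions paragraph says what the fluoride figure is for: "The total urinary recovery of fluoride, adjusted for baseline levels, will be calculated to estimate the minimum amount absorbed in each patient". The same paragraph expects little silver in urine and promises no adjustment for it.

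The protocol collects material for the adjustment. Under Baseline procedures: "Subject will void for a baseline urine sample collection". Under sample processing: "The total volume of urine at baseline, 12 and 24 hours will be recorded and a 10 mL aliquot will be taken of each sample". Sample Analysis has urine assayed for fluoride and silver, but gives no formula for recovery.

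The SAP gives the formula: "The total urinary recovery of fluoride and silver will be determined by multiplying the concentration measured in the urine collected over 24 hours", times the 24-hour urine volume. Its one baseline rule is confined to serum: "baseline serum fluoride and silver concentrations will be assessed and when appropriate, subtracted from other timed serum concentrations to adjust for baseline levels".

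**The concern.** Fluoride is excreted in urine whether or not the product has been applied, so concentration times volume over 24 hours counts background as well as treatment-related fluoride. The protocol wants the second part only. The SAP corrects serum AUC for baseline and reports Cmax both observed and corrected, but gives urine no such treatment.

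The design does not remove background. On toothpaste the protocol says: "Non-fluoride toothpaste will be used on the day of the baseline appointment through the 24-hour blood draw period". It also excludes users of fluoride gels or rinses, bars eating for 2 hours after application, and keeps subjects on site for 12 hours. None of this limits fluoride from water, or from food after the first 2 hours.

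At stake is whether a named PK parameter can serve its stated use. A figure containing an unknown amount of background cannot validly be read as a minimum absorbed, and with so little fluoride applied the background may be a large part of it.

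**Working it through.** The documents state no urinary recovery figure, so there is none to reproduce. The check compares the two definitions and then sizes the gap.

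**1. Definitions**

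- SAP: R_gross = C(0–24) × V(0–24)
- Protocol, for fluoride: R_net = R_gross − B, where B is 24-hour background excretion
- Difference: R_gross − R_net = B. This is positive whenever any background is excreted.

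**2. Applied fluoride**

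The Study intervention section gives 5 mg of product at 5.0–5.9% (w/v) fluoride. Reading w/v as w/w (density 1.0 g/mL assumed):

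- 5 × 0.050 = 0.25 mg
- 5 × 0.059 = 0.295 mg

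At an assumed density of 1.3 g/mL the range is 0.19–0.23 mg. The actual amount is weighed for each subject. For a larger dose I use the preliminary study in the protocol's Background: "Mean amount of the agent applied was 7.57 mg". At 5.9% that is 7.57 × 0.059 = 0.447 mg.

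**3. Background share**

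The documents give neither B nor the fraction f of applied fluoride excreted in 24 hours. I assume B = 0.05–1.0 mg/24 h and f = 0.5 or 0.3.

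- Share of the reported figure that is background = B / (B + f × dose)
- Reported figure exceeds applied fluoride when B > (1 − f) × dose

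| Dose (mg F) | f | f × dose (mg) | Share at B = 0.05 | Share at B = 1.0 | Exceeds dose when B > |
|---|---|---|---|---|---|
| 0.25 | 0.5 | 0.125 | 0.05/0.175 = 29% | 1.0/1.125 = 89% | 0.125 mg |
| 0.25 | 0.3 | 0.075 | 0.05/0.125 = 40% | 1.0/1.075 = 93% | 0.175 mg |
| 0.447 | 0.5 | 0.223 | 0.05/0.273 = 18% | 1.0/1.223 = 82% | 0.223 mg |

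In the first row the reported figure is 0.175/0.125 = 1.4 to 1.125/0.125 = 9.0 times the treatment-related amount.

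**4. The same gap from concentrations**

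Assume 1.5 L of urine per 24 hours, 0.295 mg applied and half excreted (0.1475 mg).

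- Background 0.05 mg/L: 0.075 + 0.1475 = 0.223 mg reported, 75% of dose
- Background 0.1 mg/L: 0.15 + 0.1475 = 0.297 mg, 101% of dose
- Background 1.0 mg/L: 1.5 + 0.1475 = 1.647 mg, 558% of dose

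The net amount is 50% of dose in all three.

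**5. Is correcting with one void better than not correcting?**

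Suppose the baseline concentration is 30% off the true 24-hour background concentration (assumed). The error left in net recovery is 0.3 × B, which is 0.015 mg at B = 0.05 and 0.30 mg at B = 1.0. The uncorrected bias is 0.05 and 1.0 mg. With 0.125 mg treatment-related fluoride, net could turn negative when 0.3 × B > 0.125, that is, B above about 0.42 mg/24 h.

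**The case against.** The strongest reply is that the SAP bullet merely defines a gross quantity. It matches the unadjusted term in the protocol's Objective, the SAP never calls it a minimum absorbed, and silence does not withdraw the protocol's adjustment. That reading is possible, but it leaves the promised net estimate with no analysis in the SAP, and the repair is the same.

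Other points have some force:

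- Gross recovery could still lie below the amount absorbed if background is smaller than the absorbed fluoride not excreted by 24 hours. With all 0.25 mg absorbed, 0.125 mg excreted and B = 0.05 mg, gross is 0.175 mg. True, but nothing in the SAP would show whether a given subject is in that position.
- The size rests on assumptions. The preliminary 7.57 mg was for three teeth and this protocol treats five; proportional scaling (an assumption, at odds with the nominal 5 mg) gives 7.57 × 5/3 = 12.6 mg, or 0.744 mg fluoride at 5.9%. With half excreted the share is 12% to 73%. This stands: only the direction is settled.
- One untimed void is a weak baseline. If it is more than twice as concentrated as the true 24-hour background, the correction adds more error than it removes. This also stands, and is why gross should be reported beside net.
- The analysis is descriptive, and overstating exposure is cautious for safety. That tempers the severity, but overstatement is the wrong direction for a quantity meant as a minimum.
- The 24-hour urine might be pooled before sampling. The second container and the separate 12- and 24-hour volumes and aliquots point to two intervals, though the text could be clearer.

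**Conclusion.** The concern holds. As written, the SAP computes something other than the fluoride quantity the protocol describes, and it should be corrected. This conclusion rests on the text alone and I hold it with high confidence.

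The bias equals each subject's 24-hour background excretion and is upward. Across the three main scenarios, background is between 18% and 93% of the reported figure. Whether it is the larger part depends on the assumed background, excreted fraction and dose, none of which the documents settle.

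The contradiction is confined to fluoride. How the 12- and 24-hour aliquots become one concentration needs clarifying but is not a shown error: a volume-weighted value would be exact.

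**What to change.** For fluoride, replace the SAP bullet with wording such as:

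> Gross recovery = C(0–12) × V(0–12) + C(12–24) × V(12–24). Net recovery = gross recovery minus baseline urine fluoride concentration × 24-hour urine volume. Because the baseline void is untimed, net recovery is reported as an approximation. Gross and net are both reported; only net is used as the estimate of the minimum absorbed.

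If the time of the preceding void was recorded, or can still be added, subtract baseline excretion rate × 24 h instead. If the two collections are in fact pooled before sampling, gross is the single product of concentration and volume, and the subtraction is unchanged. State that negative net values are kept as calculated; setting them to zero would push the mean upward again. Doing the same for silver is optional.

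The cost is SAP wording only, using samples, volumes and aliquots already planned. The price is a smaller and noisier figure, possibly negative in some subjects, that assumes the baseline concentration represents background over the following 24 hours.
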